The purpose of this study is to determine whether using CBCT to perform an abdomen-pelvis CT scan immediately following initial PCNL, before the patient emerges from general anesthesia, allows the surgeon to determine whether additional work is needed or whether the procedure can be concluded without requiring further imaging or future interventions. Therefore, the primary outcome will be the rate of subsequent surgical intervention (i.e. "second-look" interventions) in patients undergoing CBCT.

IV. Administrative Organization

This study will be performed exclusively in the Main Operating Room area of Loyola University Medical Center.

V. Study Design

1. The study population will be patients undergoing initial PCNL, and they will be recruited to participate in this study prior to surgery.
2. Outcomes from this study will be compared with existing data on rates of second-look intervention at this institution.
3. **Our retrospective chart review of PCNL patients from 2018 and 2019 revealed a total of 178 PCNL patients, with a second-look intervention rate of 31.5%. We anticipate that use of CBCT will reduce our second-look intervention rate to 10%. However, despite being rendered radiographically stone-free with CBCT, we imagine patients may require second-look procedures for various reasons; we estimate the upper bound of this occurrence to be 15%. Assuming this, along with a power of 80% and a type I error rate of 5%, our study would be appropriately powered with 39 patients. We will aim to recruit 60 patients to allow for redundancy and unanticipated exclusions such as for reasons listed in VI.1.i.2.**

VI. Study Procedures

1. Subject selection procedures
 - i. Sampling plan
 1. Inclusion criteria:
 - a. Patients >18yo
 - b. Undergoing initial PCNL
 - c. **Stone fragmentation (laser/ultrasonic/mechanical) was performed during the procedure**
 2. Exclusion criteria:
 - a. **Patients who are deemed by the operating surgeon not to require any form of CT imaging, intra-operatively or post-operatively (for example, this can occur in the event of a single visible stone which is removed in its entirety under direct vision without requiring any fragmentation)**
 - b. Patients whose procedures are aborted for various reasons, including but not limited to bleeding, hemodynamic instability, equipment failure, and inadequacy of nephrostomy access
 - c. Patients whose habitus does not allow for the use of the CBCT machine
 - ii. Recruitment procedures

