 1. **Patients undergoing initial PCNL will be recruited and provided protocol/consent materials at a preoperative**

outpatient clinic visit. Consent will be obtained by one of the research team members at the preoperative visit or in the preoperative area on the day of surgery.

2. The patient will not be required to attend any additional clinical appointments beyond standard care. The patient will not be compensated for their participation in the study.
2. Data collection procedures
 - i. **A retrospective chart review of first-look PCNL procedures from 2018-2019 will be performed to identify a matched-cohort (based on patient demographics and stone characteristics) that meets the inclusion and exclusion criteria.**
 - ii. Data will be prospectively collected for our study cohort. The determination of our primary outcome (need for repeat surgical intervention) will be made in our usual fashion: via shared decision-making between the patient and the surgical team on the day subsequent to the initial procedure.
 - iii. Data collected for both cohorts will include but not be limited to:
 1. Demographic factors (age, sex, race/ethnicity)
 2. Medical factors (patient height and weight, presence of medical comorbidities, surgical history, pertinent laboratory values)
 3. Stone factors (location, size, composition, and other characteristics)
 4. Surgical factors (length of procedure, blood loss, operative time, length of hospital stay, radiation dose)
 5. Surgical complications, ranked by Clavien-Dindo class
 - iv. All data will be entered into Loyola's secure RedCAP application.

VII. Safety Monitoring Plan

1. There are no additional anticipated patient safety issues associated with performing intra-operative CBCT when compared to standard post-operative CT imaging.
2. In another study using the same Medtronic O-arm CBCT system that is available at Loyola, it has been demonstrated that the radiation dose experienced by the patient from CBCT is lower than that from standard CT imaging.⁴

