3. In regards to radiation safety for operating room staff, standard precautions will be taken which include but are not limited to: using lead aprons for sterile surgical staff, optimizing the placement of sterile and non-sterile surgical staff, using lead aprons for sterile surgical staff, and standing beyond a 2-meter distance from the iso-centre. Assuming one CT per surgical procedure, a liberal average of three procedures per week, and 48 work-weeks per year, an unprotected staff member would be expected to receive below 1.6 mSv a year at a distance of 2-meters from the iso-centre.⁴ This is far below the occupational exposure limit set at 50 mSv per year by OSHA (Occupational Safety and Health Administration).

VIII. Analysis Plan

1. The historical cohort and study cohort will be compared on a variety of demographic and surgical factors to ensure homogeneity between the groups. Chi-squared and Student's t-tests will be performed as appropriate.
2. The proportion of patients requiring a second-look procedure would be calculated for both our cohort under study and our historical cohort. These proportions would be analyzed with a chi-squared test to determine statistical significance.
3. We would also perform subgroup analyses on a variety of patient characteristics, including but not limited to BMI, stone size, stone composition, and stone location, to determine if certain patient populations are more likely to benefit from CBCT.
4. Data will be analyzed by exporting tables from RedCAP onto Loyola's secure research network drives. From there, data will be imported into SPSS and analyzed as appropriate by the research team.

IX. Literature Cited

1. Pearle MS, Watamull LM and Mullican MA: Sensitivity of noncontrast helical computerized tomography and plain film radiography compared to flexible nephroscopy for detecting residual fragments after percutaneous nephrostolithotomy. *J Urol* 1999; 162: 23.

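### The operating surgeon is neither matched on, listed, checked nor adjusted for, so a change in surgeon mix since 2018-2019 could be mistaken for a CBCT effect or could hide one

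*Combined protocol and SAP*

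**What the plan says.** - **Comparator.** Section VI.2.i: "A retrospective chart review of first-look PCNL procedures from 2018-2019 will be performed" to find a "matched-cohort (based on patient demographics and stone characteristics) that meets the inclusion and exclusion criteria". Section V.3 reports from the earlier chart review "a total of 178 PCNL patients, with a second-look intervention rate of 31.5" per cent.
- **Outcome.** Section VI.2.ii: the need for a repeat intervention is settled "via shared decision-making between the patient and the surgical team on the day subsequent to the initial procedure".
- **Data items.** Section VI.2.iii opens with "Data collected for both cohorts will include but not be limited to", then names demographic, medical, stone and surgical factors and complications. Item 4 reads "Surgical factors (length of procedure, blood loss, operative time, length of hospital stay, radiation dose"; the operating surgeon is not there.
- **Balance check.** Section VIII.1: the cohorts are "compared on a variety of demographic and surgical factors to ensure homogeneity between the groups". The factors are not listed, and nothing is said about what follows if the groups differ.
- **Primary test.** Section VIII.2: "These proportions would be analyzed with a chi-squared test to determine statistical significance". No covariate or stratum is given. The subgroup list in VIII.3 does not name surgeon either.

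**The concern.** The surgeon can influence a second-look rate in two ways: through how much stone is cleared at the first procedure, and through how readily a second look is advised. The first is general to surgery. The second is a reasonable inference from VI.2.ii, which makes the surgical team a party to the decision. Surgeon judgement also affects who is counted, since exclusion VI.1.i.2.a turns on whether the operating surgeon thinks CT is needed.

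The comparison is not concurrent: 2018-2019 charts against patients enrolled under a protocol dated August 2021. Staffing and the split of cases between surgeons may have changed in between. Matching on patient and stone features does not balance surgeons, and an unadjusted test attributes any remaining difference to CBCT. At stake is the only primary comparison in the study.

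**Working it through.** **Is surgeon covered anywhere?** Matching (VI.2.i): not named. Data list (VI.2.iii): not named, but the list is open. Balance check (VIII.1): not named. Primary test (VIII.2): no adjustment. Subgroups (VIII.3): not named. So the plan may allow surgeon to be recorded, but it nowhere commits to recording it or using it.

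**How large could the effect be?** The plan states no figure on this point, so there is none to reproduce.

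Inputs from the documents: historical rate 31.5%, 178 historical patients, 60 CBCT patients to be recruited (V.3).

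Assumptions: two surgeons with rates a < b, each doing half the historical cases, so (a + b)/2 = 31.5%; no CBCT effect; surgeon rates constant over time. The gap b - a is the difference that remains after matching on patient and stone features.

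If the lower-rate surgeon does a share s of study cases, the expected study rate is s·a + (1 - s)·b, and the spurious reduction is (s - 0.5)(b - a). With s = 0.8:

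- 25% and 38%: 0.8 × 25 + 0.2 × 38 = 27.6%; reduction 0.3 × 13 = 3.9 points
- 20% and 43%: 0.8 × 20 + 0.2 × 43 = 24.6%; reduction 0.3 × 23 = 6.9 points
- 15% and 48%: 0.8 × 15 + 0.2 × 48 = 21.6%; reduction 0.3 × 33 = 9.9 points

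For each study rate, the binomial probabilities of all outcome pairs giving an uncorrected chi-squared p < 0.05 in favour of CBCT were summed, with a control rate of 31.5%. Two control sizes are shown because VI.2.i does not say how many matched controls there will be.

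| Surgeon rates, share s | Study rate | 60 v 60 | 60 v 178 |
|---|---|---|---|
| Mix unchanged | 31.5% | 2.6% | 2.3% |
| 25% / 38%, 80% | 27.6% | 7% | 7.6% |
| 20% / 43%, 80% | 24.6% | 13.6% | 16.1% |
| 15% / 48%, 80% | 21.6% | 24% | 30% |
| 20% / 43%, 100% | 20.0% | 30.9% | 39.6% |
| 20% / 43%, reverse (20%) | 38.4% | 0.3% | 0.2% |

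With the 39 CBCT patients of the sample-size statement against 178, the 24.6% case gives 12%.

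In the reverse row (0.2 × 20 + 0.8 × 43 = 38.4%), the study cohort starts 6.9 points above the historical rate, so a real benefit would be partly hidden.

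**Does stratifying remove it?** In this set-up, yes. Within the first surgeon the comparison is 20% against 20%, within the second 43% against 43%. Each within-surgeon difference is zero whatever the mix.

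**The case against.** The strongest reply is that nothing shows the surgeon mix changed, or that there is more than one surgeon. That stands: this is a risk of unknown size and direction. Even the 6.9-point shift is well below the planned difference of 16.5 to 21.5 points (31.5% less 15% or 10%).

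The data list is also open, and the balance check speaks of surgical factors in general. Both leave room for surgeon. Neither commits the team to recording it, and a balance test with no stated consequence corrects nothing.

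A reader might infer three stronger points, which the documents do not support:

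- *That all 178 earlier patients are the comparator.* V.2 refers to existing institutional data, and V.3 uses the 178 in the sample-size paragraph. But VI.2.i describes a matched cohort meeting the eligibility criteria. The 178 serves above only as an upper limit on the control pool.
- *That only surgeons who use CBCT will contribute study patients.* No section restricts recruitment by surgeon; VI.1.ii.1 refers to patients having an initial PCNL.
- *That the gap cannot be repaired later.* This would hold only for the variables listed. Surgeon should be recoverable from operative notes for both cohorts.

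Finally, VI.2.ii speaks of a surgical team and a patient, and section II says the decision rests on CT findings. The operating surgeon is naturally part of that team, but a personal threshold for advising a second look is inferred.

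**Conclusion.** The omission is real and its consequence conditional. Surgeon is not named at any stage from matching to analysis, in a non-concurrent, unadjusted comparison of an outcome that the surgical team helps to decide. If the mix changed and surgeons' rates differ beyond what matching removes, the bias goes straight into the primary result, in either direction.

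Under the two-surgeon assumptions with an 80% share and 60 against 178, a false significant benefit has a probability of about 8% for a 13-point gap and 16% for a 23-point gap, against 2.3% with the same mix. These figures show sensitivity; they do not estimate what happened at this institution. The point deserves correction because the remedy is cheap, not because bias has been shown.

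**What to change.** 1. **VI.2.iii.4:** add a coded operating-surgeon ID for both cohorts, taken from the operative note.
2. **VIII.1:** name surgeon in the balance comparison.
3. **VIII.2:** report second-look rates by surgeon and period, and add a surgeon-stratified (Mantel-Haenszel) or surgeon-adjusted comparison beside the chi-squared test.
4. **VI.2.i:** match on surgeon only where the control pool allows. Exact matching on surgeon, on top of demographics and stone features, in a pool of at most 178 could leave CBCT patients without a control, so it should not be mandatory.

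If one surgeon performed all procedures in both periods, a sentence saying so settles the point.

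Cost: one extra field and slightly less precision. Cases of a surgeon with no 2018-2019 PCNLs contribute nothing to the stratified estimate and must be reported separately. No extra patients, visits or changes in care are needed.

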Protocol Outline

Protocol Title: Intraop Cone-beam CT for Percutaneous Nephrolithotomy

Protocol Date: August 23, 2021

Principal Investigator: [name], [name]

Research Team: [name], [name]

I. Abstract

Percutaneous nephrolithotomy (PCNL) is a first-line treatment for kidney stones >2cm. Frequently, patients require multiple procedures to address their stone burden. The decision to proceed with a second-look procedure is based on follow-up CT imaging, which is obtained postoperatively. In this study, we propose the use of a portable CT scan technology to obtain follow-up imaging while the patient is still under anesthesia for the initial procedure. The goal of this study is to determine whether this allows the surgeon to identify residual fragments and render the patient stone-free within a single anesthetic event.

II. Background and Significance/Preliminary Studies

Percutaneous nephrolithotomy (PCNL) is considered a first-line management option for kidney stones larger than two centimeters. Unfortunately, because of the large stone burden, up to 70% of these patients are left with residual stone fragments after their initial PCNL.¹ Additionally, an estimated 20% to 60% of such patients ultimately require further interventions due to residual stone fragments.² The need for a subsequent procedure is determined by postoperative abdominal computed tomography (CT) imaging, which is routinely performed on the first postoperative day at this institution. The decision to proceed with a second procedure is based on findings from this postoperative CT scan.

Cone-beam CT (CBCT) is a novel portable imaging technique that can allow cross-sectional imaging to be obtained intraoperatively, rather than post-operatively.³ Incorporating this modality would allow the surgeon to determine whether the procedure should be continued, in the event of residual fragments, or if it can be safely concluded. This would obviate the need for dedicated postoperative CT scans and, more importantly, reduce the need for subsequent procedures and consequently decrease the patient's length of stay.

III. Study Aims

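### The primary outcome is aimed at subsequent interventions but determined as a next-day decision on need, with no rule for performed procedures, and the status of the day-1 CT in CBCT patients is unclear

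*Combined protocol and SAP*

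**What the plan says.** Section III (Study Aims) states that "the primary outcome will be the rate of subsequent surgical intervention", meaning second-look interventions. It frames the aim as learning "whether the procedure can be concluded without requiring further imaging or future interventions".

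Section VI.2.ii then describes how the outcome is obtained: "The determination of our primary outcome (need for repeat surgical intervention) will be made in our usual fashion", namely "via shared decision-making between the patient and the surgical team on the day subsequent to the initial procedure". Section VIII.2 compares the proportions requiring a second look in the study and historical cohorts with a chi-squared test.

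Section V.3 gives the historical figure, a second-look intervention rate of 31.5% among 178 patients from 2018 and 2019, without saying how or over what period second looks were counted. It anticipates 10% with CBCT and takes 15% as an upper bound.

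On imaging, section II says of the postoperative CT "which is routinely performed on the first postoperative day at this institution", and adds: "The decision to proceed with a second procedure is based on findings from this postoperative CT scan". It describes CBCT as allowing "cross-sectional imaging to be obtained intraoperatively, rather than post-operatively", and says: "This would obviate the need for dedicated postoperative CT scans". Section VI contains no imaging schedule for CBCT patients.

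**The concern.** A rate of interventions and a next-day decision on need are different measurements. A patient can be judged to need a second look and not have one, or can have one that nobody foresaw on day 1. The plan does not say which of these counts, so a mismatch between the cohorts could act in either direction.

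The more serious possibility has one direction. The usual second-look decision rests on the day-1 CT. If CBCT replaces that scan, the intervention also removes the test that prompted the endpoint in the historical patients. Fewer positive decisions on day 1 could then reflect less postoperative imaging as well as better stone clearance. No further scan is described after any additional stone removal that the CBCT prompts, so fragments left at that stage might come to light only after the outcome has been fixed. The decision is also unblinded: the surgical team knows the CBCT result. A fall in the rate could not then be credited wholly to clearance.

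**Working it through.** **Step 1. Set the passages side by side.**

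| Element | Where | Content |
|---|---|---|
| Outcome in the aims | III | Rate of subsequent surgical intervention |
| Outcome as determined | VI.2.ii | Need for repeat intervention, shared decision, day after surgery |
| Outcome as analysed | VIII.2 | Proportion requiring a second look, both cohorts |
| Historical rate | V.3 | 31.5% of 178, counting rule not stated |
| Basis of the usual decision | II | Routine day-1 CT |
| Day-1 CT after CBCT | II, III, VII.1–2 | Expected to be unnecessary; CBCT compared with standard CT as an alternative |
| Day-1 CT after CBCT | VI.2.ii | Usual process kept, which by II rests on that CT |

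The decision has a person, a method and a day. Three things are absent: whether decided or performed procedures count, a window for performed procedures, and the counting rule behind the 31.5%. The last two rows point in opposite directions, and neither is a procedural statement about imaging.

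**Step 2. Follow each reading.**
- *Day-1 CT kept, one counting rule for both cohorts:* both decisions use the same scan on the same day, and the concern largely disappears.
- *Day-1 CT dropped:* the CBCT cohort's decision is made without the scan behind the historical one. Second looks recognised later are neither included nor excluded by the text, so the CBCT rate could be too low.

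**Step 3. Scale.** The documents give nothing from which to estimate the bias. What can be calculated is how many added CBCT events would remove significance.

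Inputs: 178 patients, 31.5%, 10%, 15% and a recruitment target of 60 (V.3); chi-squared test (VIII.2). Assumptions: two-sided 5% level, no continuity correction, all 60 analysed, historical count held fixed.

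The plan's own figure: 0.315 × 178 = 56.07, and 56/178 = 31.46%, which rounds to 31.5% (55 gives 30.9% and 57 gives 32.0%).

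With *a* events among 60 CBCT patients, *b* = 60 − *a*, and historical counts 56 and 122:

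χ² = 238 × (122*a* − 56*b*)² / [60 × 178 × (*a* + 56) × (*b* + 122)], with critical value 3.84.

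| CBCT events | 122*a* − 56*b* | Column totals | χ² | p |
|---|---|---|---|---|
| 6/60 (10%) | −2292 | 62, 176 | 10.73 | 0.0011 |
| 9/60 (15%) | −1758 | 65, 173 | 6.13 | 0.0133 |
| 10/60 | −1580 | 66, 172 | 4.90 | 0.0268 |
| 11/60 | −1402 | 67, 171 | 3.82 | 0.0505 |

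Significance is lost at 11/60: 11 − 6 = 5 added events from 10%, and 11 − 9 = 2 from 15%. A continuity correction gives p = 0.0407 at 10/60 and 0.0736 at 11/60, so the counts of five and two do not change.

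The tolerance shrinks with smaller groups. With 39 CBCT patients, 6/39 gives p = 0.0441 and 7/39 gives p = 0.0922, so one event suffices near 15%. Section VI.2.i plans a matched cohort of unstated size. If matching were 1:1 (an assumption), 9/60 against 19/60 gives p = 0.0309 and 10/60 gives p = 0.0550, again one event.

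**The case against.** The strongest defence is that VI.2.ii does supply a rule. It says who decides, how and on which day, and a fixed day is a time rule for a decision endpoint. The reference to the usual process, the comparison with the same institution's data in V.2 and the single phrase in VIII.2 all suggest one rule for both cohorts. The chart review in VI.2.i has still to build the comparator, so the 31.5% may be only a planning figure. This stands in part. A reader might infer that the endpoint has no rule at all, or that the historical rate was counted differently; the documents support neither. But a shared decision process does not show whether the charts were counted for decisions or for procedures performed.

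A second defence is that moving the imaging into the anesthetic is the strategy under test, so different information on day 1 is not in itself an error. That is fair, and nothing suggests that the historical decision was blinded either. It does not answer the case in which a missed fragment leads to a procedure after the outcome has been fixed, although section III names avoidance of future interventions as the aim.

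Third, the bias is conditional, and the event counts in the working measure small-sample fragility rather than this defect. Both points stand. A wider window could also add historical events, which would increase the tolerance.

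**Conclusion.** The concern holds in a conditional form and should be fixed. It is certain that the plan does not say whether decided or performed second looks count, sets no window for performed procedures, does not state how the 31.5% was counted, and leaves the day-1 CT unresolved for CBCT patients. Followed as written, VI.2.ii can ascertain the two cohorts on different information.

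The direction and size are less certain. Downward bias in the CBCT rate requires that the day-1 CT is dropped and that later second looks go uncounted. A reader might infer from section II that the scan is definitely omitted and the result therefore biased. The text does not go that far: section II states an expectation, and VI.2.ii can be read as keeping the scan.

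The tolerance of five events at 10% and two at 15% assumes 60 analysed patients, 56/178 held fixed and an uncorrected two-sided test. It indicates scale and does not estimate the bias. Confidence is medium.

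**What to change.** Define the primary outcome in both cohorts as a repeat stone-removal procedure actually performed on the index kidney within one prespecified window after the initial PCNL, the length to be chosen by the investigators. Abstract it from records by the same rule in both cohorts, and re-count the historical rate that way during the chart review already planned in VI.2.i. If the re-count differs from 31.5%, recheck the sample size in V.3. Keep the day-1 decision as a secondary outcome.

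Reconcile sections II, III, VI.2.ii and VII on whether CBCT patients have the day-1 CT. Report postoperative CT use by cohort, and state any remaining differential-imaging bias as a limitation.

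If the investigators prefer to keep the day-1 decision as primary, the minimum is to state whether decided or performed procedures count, apply that identically to both cohorts, and reconcile the imaging passages.

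The cost is protocol wording and a short record review, with no added visit or scan. The downsides are a later final result, possible loss of procedures done elsewhere in both cohorts, and an endpoint broader than the day-1 decision. Some imaging bias may remain, and the decision behind each performed procedure is still unblinded.

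### Non-significant tests cannot show that the matched cohorts are comparable, and the check does not name the stone characteristics used for matching

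*Combined protocol and SAP*

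**What the plan says.** Section VIII, item 1: "The historical cohort and study cohort will be compared on a variety of demographic and surgical factors to ensure homogeneity between the groups". The method is chi-squared and Student's "t-tests will be performed as appropriate". The item gives no measure of balance, no threshold, and no action if a factor differs. Item 2 then compares the second-look proportions with an unadjusted chi-squared test.

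VI.2.i provides for a historical control group matched on demographics and on stone characteristics and meeting the same eligibility criteria. It does not state the matching ratio, method or tolerance.

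VI.2.iii lists the data for both cohorts in separate groups: demographic, medical, stone and surgical factors, and complications. The stone group reads "Stone factors (location, size, composition, and other characteristics"). The surgical group covers operating time, bleeding, hospital stay and radiation dose.

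V.3 gives the planning figures. The 2018-2019 review "revealed a total of 178 PCNL patients", and 31.5% of them had a second look. On the effect of CBCT the section says: "We anticipate that use of CBCT will reduce our second-look intervention rate to 10"%. For patients who still need a second look it adds: "we estimate the upper bound of this occurrence to be 15"%. The powered size is 39 and the recruitment target is 60.

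**The concern.** The comparison is not randomised, so its credibility depends on whether the two cohorts had similar chances of a second look before surgery. VIII.1 tries to settle this with significance tests, which raises three difficulties.

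- **The p-value depends on sample size as well as on balance.** The smaller the matched set, the easier it is to find no significant difference.
- **The surgical factors are not baseline factors.** They are recorded during or after the operation. The Background expects CBCT to affect whether the procedure continues and to shorten the stay. A difference in these factors may be an effect of CBCT, and similarity says nothing reliable about case mix.
- **Stone factors are not named in the check**, although VI.2.i matches on them. In the Analysis Plan they appear only as subgroups (VIII.3).

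At stake is how the primary result is read. If the stone burden differs between cohorts and the check does not reveal it, part of any difference in second-look rate is case mix, and the unadjusted test attributes it to CBCT.

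**Working it through.** **Inputs from the documents (V.3).** Study cohort 39 or 60; historical cohort 178 before matching; historical rate 31.5%; CBCT rate 15% or 10%. The contrasts are 31.5 − 15 = 16.5 points and 31.5 − 10 = 21.5 points. The matched size is not stated, so 1:1 matches and the full 178 are both shown.

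**Assumptions.** Balance tests two-sided at 5% (sidedness is not stated). True imbalance 0.3 SD. Odds ratio for second look 1.5, 2 or 2.5 per SD of stone burden; the documents give no prognostic strength.

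**Step 1. The plan's own figure.** VIII.1 contains no figure to reproduce. The 39 used here as a cohort size is closely matched by a one-sided, one-sample arcsine formula for 31.5% vs 15% at 80% power: (1.645 + 0.842)² / (2·arcsin√0.315 − 2·arcsin√0.15)² = 39.3.

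**Step 2. What the t-test can see.** SE of a standardised difference = √(1/n₁ + 1/n₂). Noncentrality = 0.3/SE. Power comes from the noncentral t with n₁ + n₂ − 2 degrees of freedom. The largest observed difference that stays non-significant is the critical t times SE.

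| Study vs historical | SE | 0.3/SE | Power to flag 0.3 SD | Largest non-significant difference |
|---|---|---|---|---|
| 39 vs 39 | 0.226 | 1.32 | 26% | 0.45 SD |
| 60 vs 60 | 0.183 | 1.64 | 37% | 0.36 SD |
| 39 vs 178 | 0.177 | 1.70 | 39% | 0.35 SD |
| 60 vs 178 | 0.149 | 2.01 | 52% | 0.29 SD |

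**Step 3. What a missed imbalance does.** Take logit(risk) = a + ln(OR)·x, with x standard normal in the historical cohort and a solved so that the mean risk is 31.5%. Then lower the mean of x by 0.3, with no CBCT effect.

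| OR per SD | a | Rate after shift | Shift (points) | Share of 16.5 | Share of 21.5 |
|---|---|---|---|---|---|
| 1.5 | −0.806 | 29.02% | 2.48 | 15% | 12% |
| 2.0 | −0.858 | 27.55% | 3.95 | 24% | 18% |
| 2.5 | −0.912 | 26.61% | 4.89 | 30% | 23% |

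A shift the other way (heavier stones in the study cohort) raises the rate by a similar 2.6 to 5.3 points and would hide benefit.

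**Step 4. Which factors are checked.**

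| Group in VI.2.iii | Matched on (VI.2.i) | Named in VIII.1 | Fixed before surgery |
|---|---|---|---|
| Demographic | yes | yes | yes |
| Medical | no | no | yes |
| Stone | yes | no | yes |
| Surgical | no | yes | no |

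Only the demographic group is matched on, named in the check and fixed before surgery.

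**Step 5. Would an automatic 0.1 SMD rule work instead?** With no true imbalance and no help from matching, the chance of |SMD| > 0.1 is 2·[1 − Φ(0.1/SE)]: 66%, 58%, 57% and 50% in the order of the first table. With ten factors at 60 vs 60, about 10 × 0.58 = 5.8 would exceed 0.1. Expected events at 60 vs 60 are 60 × 0.315 + 60 × 0.15 = 18.9 + 9.0 ≈ 28. Six such terms plus cohort leave 28/7 = 4 events per term. Two prespecified stone factors plus cohort leave 28/3 ≈ 9.

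**The case against.** The strongest reply is that matching under VI.2.i is the main device for comparability and VIII.1 is a descriptive check after it. That stands. A reader might infer that VIII.1 is the plan's only safeguard, and the documents do not support this. Nor do they show that a 0.3 SD stone imbalance would survive matching; the power figures are conditional on one existing. What remains is that the matching method is unspecified and the planned check could not show whether it worked.

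A reader might also infer that the tests will usually pass cohorts that differ materially. That is too strong: at 60 vs 178 a 0.3 SD imbalance is flagged slightly more often than not (52%). VIII.1 also states no pass/fail rule. The difficulty lies in its stated aim of securing homogeneity by these tests.

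The wording of VIII.1 is open-ended, so stone factors are unnamed and not excluded. An analyst could check them, but could also omit them and still comply.

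Finally, the effect sizes rest on an assumed prognostic strength, and the bias could run either way. Both points stand and limit what can be claimed.

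**Conclusion.** The concern holds in this limited form. The tests in VIII.1 cannot establish comparability: power to flag a 0.3 SD imbalance is 26% to 52% across the cohort sizes the plan allows, lowest for a 1:1 match at 39. One of the two groups of factors named can be affected by CBCT, and the stone factors used for matching are not named. The unadjusted test in VIII.2 does not correct for what is missed.

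If a 0.3 SD imbalance in stone burden remained after matching, it would move the second-look rate by about 2.5 to 4.9 points, in either direction. That is 15-30% of the 16.5-point contrast, or 12-23% of the 21.5-point contrast. These shares assume an odds ratio of 1.5 to 2.5 per SD. The calculation does not support reading one missed factor as producing the whole planned effect, or the bias as necessarily favouring CBCT. The plan should be changed, but the point does not by itself invalidate the comparison.

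**What to change.** Replace VIII.1 with the following:

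- After matching, and before patient-level second-look outcomes are merged into the analysis file, report standardised mean differences for named pre-operative factors: stone size, stone location and other recorded stone characteristics, BMI, comorbidity, surgical history, age, sex, and race/ethnicity. Do not use p-values as evidence of comparability.
- Use an SMD of 0.1 as a guide for refining the match, not as an automatic trigger for model terms.
- Report intra-operative and post-operative surgical factors as outcomes, not as balance checks.

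In VIII.2, prespecify adjustment of the primary comparison for one or two key stone factors, for example stone size, in a small logistic model.

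The cost is revised wording, one table and one small model. VI.2.iii already collects demographic, medical and stone data in both cohorts. Stone number and complexity are not named there, so they should be added explicitly if wanted. The number of adjustment terms must stay low, because only about 28 events are expected at 60 vs 60. Some SMDs will exceed 0.1 by chance, and the report should say so.
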